8 PARTICIPANT IDENTIFICATION

8.1 Trial Participants

Healthy UK adults who are latently infected with *M.tb* and have no evidence of active disease.

8.2 Inclusion Criteria

Volunteers must meet all of the following criteria to enter the trial:

- Healthy adult aged 18-55 years
- Resident in or near Oxford, Birmingham or London for the duration of the trial period

- Screening IGRA positive
- Considered low risk of reactivation of their latent infection due to distant contact history
- Chest CT normal; or abnormal with features consistent with primary *M.tb* infection but no features suggestive of active disease
- No relevant findings in medical history or on physical examination
- Allow the Investigators to discuss the individual's medical history with their GP
- Use effective contraception (see below) for the duration of the trial period (females only)
- Refrain from blood donation during the trial.
- Give written informed consent
- Allow the Investigator to register volunteer details with a confidential database (The Over-volunteering Protection Service) to prevent concurrent entry into clinical trials
- Able and willing (in the Investigator's opinion) to comply with all the trial requirements

8.3 Exclusion Criteria

Volunteers must meet none of the following criteria to enter the trial:

- Participation in another research study involving receipt of an investigational product in the 30 days preceding enrolment, or planned use during the trial period^d
- Prior vaccination with candidate vaccine MVA85A, candidate vaccine FP85A, any other recombinant MVA vaccine or any other candidate TB vaccine
- Administration of immunoglobulins and/or any blood products within the three months preceding the planned trial vaccination date
- Clinically significant history of skin disorder, allergy, atopy, immunodeficiency (including HIV), cancer (except BCC or CIS), cardiovascular disease, gastrointestinal disease, liver disease, renal disease, endocrine disorder, neurological illness, psychiatric disorder, drug or alcohol abuse
- Concurrent oral or systemic steroid medication or the concurrent use of other immunosuppressive agents
- History of anaphylaxis to vaccination or any allergy likely to be exacerbated by any component of the trial vaccine, sedative drugs, or any local or general anaesthetic agents
- Pregnancy, lactation or intention to become pregnant during trial period
- Any respiratory disease, including asthma
- Current smoker
- Clinically significant abnormality on screening CT thorax^{a, b}
- Clinically significant abnormality of pulmonary function tests^b
- Any nasal, pharyngeal, or laryngeal finding which precludes bronchoscopy
- Current use of any medication taken through the nasal or inhaled route including cocaine or other recreational drugs
- Clinical, radiological, or laboratory evidence of current active TB disease^c
- Past treatment for TB disease
- Any clinically significant abnormality of screening blood or urine tests^b

- Positive HBsAg, HCV or HIV antibodies^b
- Any other significant disease, disorder, or finding, which, in the opinion of the Investigator, may either put the volunteer at risk, affect the volunteer's ability to participate in the trial or impair interpretation of the trial data

^a Excepting findings felt to be consistent with latent TB infection only.

^b Volunteers who are excluded from the trial because they have been discovered during screening procedures to be suffering from a previously undiagnosed condition thought to require further medical attention will be referred appropriately to their GP or an NHS specialist service for further investigation and treatment.

^c If there is any evidence of active TB disease either on clinical or radiological grounds, further investigation and treatment will be offered under the supervision of a consultant physician in respiratory or infectious diseases.

^d Volunteers will be excluded from the trial if they are concurrently involved in another study or trial that involves regular blood tests or an investigational medicinal product. In order to check this, volunteers will be asked to provide their National Insurance or Passport number (if they are not entitled to a NI number) and will be registered on a national database of participants in clinical trials (www.tops.org.uk).

Effective contraception for female volunteers

Female volunteers are required to use an effective form of contraception during the course of the trial. There is no information about the effect of these vaccines on a fetus. Previous investigations looking at excretion of viral vectors after vaccination in urine for males, demonstrated no detectable virus; therefore males are not required to use barrier contraception whilst taking part in this study as the risk of excretion of the virus is very low.

Acceptable forms of contraception for female volunteers include:

- Established use of oral, injected or implanted hormonal methods of contraception
- Placement of an intrauterine device (IUD) or intrauterine system (IUS)
- Permanent sterilisation or bilateral tubal occlusion
- Barrier methods of contraception (condom; or occlusive cap with spermicide)
- Male sterilisation, if the vasectomised partner is the sole partner for the subject
- True abstinence, when this is in line with the preferred and usual lifestyle of the subject
(Periodic abstinence and withdrawal are not acceptable methods of contraception)

9 TRIAL DESIGN AND PROCEDURES

This is a phase I trial to evaluate the safety and immunogenicity of candidate TB vaccine MVA85A administered by the aerosol inhaled route in healthy volunteers who are latently infected with *M.tb*.

9.1 Trial Numbers and Groups

9 volunteers will be enrolled; the first 3 to the starter group, , then 3-6 volunteers into Group A.

Table 4. Trial groups

Arm of trial	Sample size	Intervention
--------------	-------------	--------------

Starter group	3	Aerosol inhaled MVA85A 1 x 10 ⁷ pfu
Group A (Standard Dose)	3-6	Aerosol inhaled MVA85A 5 x 10 ⁷ pfu

9.2 Recruitment

Volunteers considered to be at low risk of reactivation of their latent infection due to distant contact history, will be recruited from TB contact clinics at Oxford University Hospitals, Birmingham Chest Clinic Heart of England, Royal Free Hospital, King's College Hospital, Guy's and St Thomas' Hospital and St George's University Hospital. Patients who fulfil the inclusion criteria will be given a Volunteer Information Sheet Summary at their clinic attendance and asked if they would be interested in finding out more about the trial. If so, they will be given the full Volunteer Information Sheet to take with them to read in their own time. If still interested, and with their permission, the trial team will contact the patient to arrange a screening appointment. Ideally, the volunteer will delay their prospective anti-tuberculous chemoprophylaxis, provided through the usual NHS routes and TB/chest clinics, until after the trial D28 follow-up visit and CT, decision not to enrol, or early withdrawal; whichever occurs first. The study team will keep each volunteer's NHS TB/chest clinic team aware of when these timelines are reached. However, considering the challenges inherent in recruiting latently infected volunteers, if the volunteer does not want their prospective anti-TB chemoprophylaxis delayed they will still be eligible to be enrolled onto the study.

Additionally, we will send a letter to patients seen at the clinic over the previous year with a diagnosis of latent *M.tb* infection who have not been given anti-tuberculous therapy, inviting them to participate in this trial. We will also display posters in GP practices in the hope of attracting interest from latently infected individuals in the community who are no longer attending TB contact clinics.

9.3 Informed Consent

Written informed consent will be obtained at screening by a GCP trained Investigator.

The volunteer must sign and date the latest approved version of the consent form before any trial specific procedures are performed.

The Volunteer Information Sheet will be made available to the volunteer no less than 24 hours prior to attending for screening. The details enclosed will be discussed with the volunteer, including:

- the aims and nature of the trial
- the vaccines used
- the schedule of visits and tests to be carried out
- the implications and constraints of the protocol
- compensation for the volunteer
- known side effects and risks of taking part in the trial

The following general principles will be emphasised:

- Participation is entirely voluntary
- The volunteer may withdraw from the trial at any time for any reason
- Withdrawal or refusal to participate involves no penalty or loss of medical benefits
- The volunteer is free to ask questions at any time to allow him or her to understand the purpose of the trial and the procedures involved
- There is no direct benefit from participating
- The volunteer's GP will be contacted to corroborate their medical history and confirm that the volunteer does not meet any of the exclusion criteria

- The volunteer will be registered on the TOPS database (The Over-Volunteering Protection System)
- The volunteer's blood samples taken as part of the trial will be stored indefinitely for further research. The volunteer may elect to have their samples destroyed after the period required to meet Good Clinical Practice and regulatory requirements.

The volunteer will then have time to consider whether or not to participate. If the volunteer decides to participate, they will sign and date two copies of the consent form, one for them to take away and keep, and one for the Investigator which will be retained at the trial site. These forms will also be signed and dated by the Investigator or Clinical Research Nurse. This will occur before any trial specific procedures are performed.

9.4 Screening and Eligibility Assessment

Once the volunteer has given their consent to undergo screening, a baseline medical history (including concomitant medication) and physical examination will be performed by a GCP trained doctor. Inclusion and exclusion criteria will be checked using a tabulated format. Demographic and occupational data relating to risk of prior *M.tb* exposure will be collected. Vital signs will be checked and bloods taken including FBC, clotting profile, U&Es, CRP, LFTs, HIV antibodies, HBsAg, HCV antibodies and IGRA. Volunteers will be counselled by one of the Investigators for HIV, Hepatitis B and Hepatitis C testing. Urine will be tested for the presence of clinically significant proteinuria, glycosuria or haematuria. A pregnancy test will be performed for female volunteers. Volunteers will then be scheduled to re-attend for a CT thorax provided no exclusion criteria have been met.

Laboratory parameters for inclusion/exclusion in the trial will be considered on an individual basis, with Investigator discretion for interpretation of results and the need for repeated tests. In general, volunteers will be excluded if a result at screening constitutes what would qualify as a grade 1 (or higher) laboratory AE, according to the site-specific laboratory AE tables, filed in the TMF (Oxford), or Site Master File (Birmingham and London).

The total duration of the screening visit will be around 2 hours.

9.5 Follow up visits

D0 - Vaccination

Any new medical issues or symptoms that have arisen will be assessed. Venepuncture and other samples will be taken according to the Schedule of Trial Procedures in section 4.2. The inclusion and exclusion criteria for the trial will be reviewed; provided that the volunteer still satisfies all inclusion criteria (and no exclusion criteria) and their consent remains valid, the volunteer will be allocated to a group. MVA85A vaccination will be performed by the aerosol route according to the trial SOP. Volunteers will be kept under observation for around 60 minutes after vaccination. The vaccination visit will last approximately 2 hours. Volunteers will also have blood taken for HLA typing.

D7 – Bronchoscopy

The bronchoscopy visit lasts several hours and takes place at the bronchoscopy suite in the OUH NHS Foundation Trust Hospitals by the specialist team there. Details of the procedure are outlined in section 6.1. In exceptional circumstances where volunteers are absolutely unable to travel to Oxford, the bronchoscopy may be performed at the other NHS trust study sites (King's College Hospital NHS Trust, University of Birmingham NHS Trust, Royal Free Hospital NHS Trust). The bronchoscopy will always be performed by a respiratory consultant trained in the procedure and following the trial specific SOP.

D28 – CT thorax

The volunteer will usually have a clinic assessment on the same day, prior to the scan. Any abnormality reported on the CT will be appropriately investigated and followed up.

Other follow-up visits

These will be performed as specified in the Schedule of Trial Procedures (section 4.2). Any new medical issues or symptoms that have arisen will be assessed. Additional procedures or laboratory tests may be carried out at the discretion of the Investigators if deemed clinically necessary. Follow-up visits will last approximately 15-30 minutes. The maximum trial duration will be around 24 weeks after the date of enrolment.

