4.2 Schedule of visits and procedures

Table 1. Schedule of trial procedures

Attendance number	1	2	3	4	5	6	7	8
Timeline (days)*	S	0	2	7	14	28	84	168 ^T
Timeline (weeks)*	S	0		1	2	4	12	24
Time windows (days)			±1	+4, -2	±4	±7	±14	±21
Inclusion/exclusion criteria	X							
Review contra-indications	X	X		X				
Informed consent	X							
Medical history	X	(X)	(X)	(X)	(X)	(X)	(X)	(X)
Physical examination	X			X				
Vital signs	X	X	X	X	X	X	X	
Urinalysis	X							
CT chest	X					X		
PFTs	X	X	X	X	X			
β-HCG urine test	X	X		X				
Vaccinations		X						
Bronchoscopy				X				
Local & systemic events/reactions		X	X	X	X	X	X	X
Ediary setup		X						
Ediary final review					X			
Biochemistry (4mL)**	X		X	X		X		
Haematology (2mL)	X			X		X		
Coagulation (4mL)	X							
HBV, HCV, HIV (10mL)	X							
HLA typing (4mL)		X						
Exploratory immunology incl ELISpot (16-60mL***)	X	X	X	X	X	X	X	
Blood vol (mL)	30	64	20	56	60	66	60	
Cumulative blood vol (mL)****	30	94	114	170	230	296	356	

S Screening

X Event scheduled to occur

(X) If considered necessary, emphasising any complaint or change in medications

T Telephone call. Final visit is deemed to be at D84 with follow up phone call at D168

* Timeline is approximate only, as exact timings (± windows periods) of visits relate to the actual (not intended) date of the previous visit

** U&Es, LFTs (except day 2 when CRP only;)

*** 60ml at all visits except screening (10ml, T spot), visit 3 (16ml, no ELISpot) and visit 4 (50ml)

**** Blood volumes stated for Oxford. The exact volumes of blood taken will depend on the local site – cumulative blood volumes for volunteers outside Oxford may be slightly lower or higher than those of Oxford volunteers, due to the use of different volume vacutainers for biochemistry, haematology and serology samples as per local Trust standard procedures

Grey Highlights vaccination day

Blue Highlights bronchoscopy day

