9.10 Discontinuation / Withdrawal Criteria

Every reasonable effort will be made to maintain protocol compliance and participation in the trial.

In accordance with the principles of the current revision of the Declaration of Helsinki and any other applicable regulations, a volunteer has the right to withdraw from the study at any time and for any reason, and is not obliged to give his or her reasons for doing so. The Investigator may withdraw the volunteer at any time in the interests of the volunteer's health and well-being (including on the advice of the LSC). In addition the volunteer may withdraw/be withdrawn for any of the following reasons:

- Administrative decision by the Investigator
- Ineligibility (either arising during the trial or retrospectively, having been overlooked at screening)
- Significant protocol deviation
- Volunteer non-compliance with trial requirements (failure to attend two or more follow-up visits)
- Any AE which requires discontinuation of trial involvement or results in inability to comply with trial procedures
- Confirmed pregnancy during the trial

Any volunteer who becomes pregnant during the trial will be followed up as per the protocol and until the end of the pregnancy. We will not routinely perform venepuncture in a pregnant volunteer.

The reason for withdrawal will be recorded in the CRF. Volunteers withdrawn from the trial may be replaced on the decision of the Investigator. If the volunteer is withdrawn due to an AE, the Investigator will arrange for appropriate specialist management or follow up visits or telephone calls until the AE has resolved or stabilised. The regulatory authorities will be informed in a timely manner. The extent of follow up after premature discontinuation will be determined by the Investigator but will be at least for the whole trial period, and if pregnant, until pregnancy outcome.

If a volunteer withdraws from the trial, samples collected before their withdrawal from the trial will be used/stored unless the volunteer specifically requests otherwise. Long term safety data collection will continue as appropriate if a volunteer has received one or more vaccine doses.

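### Table 1 schedules no pregnancy test after D7 and before the D28 CT thorax, and no rule says that a positive result stops that scan

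*Combined protocol and SAP*

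**What the plan says.** Table 1 in section 4.2 has a row "β-HCG urine test" marked at screening, D0 and D7, and nowhere later. The CT chest row is marked at screening and D28. The row "Review contra-indications" is marked at the same three attendances as the pregnancy test and is blank at D28. Medical history at D28 is taken only if judged necessary. A footnote to the table says that "exact timings (± windows periods) of visits relate to the actual (not intended) date of the previous visit".

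For the D28 CT, section 9.5 says only that "The volunteer will usually have a clinic assessment on the same day, prior to the scan", and that any abnormality will be followed up.

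Sections 9.8 and 9.9 list a positive pregnancy test among the reasons not to proceed with vaccination and bronchoscopy. There is no corresponding list for CT.

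Section 9.10 deals with pregnancy in general. "Confirmed pregnancy during the trial" is one of the reasons for which a volunteer may be withdrawn. It adds: "Any volunteer who becomes pregnant during the trial will be followed up as per the protocol and until the end of the pregnancy". It then says: "We will not routinely perform venepuncture in a pregnant volunteer". CT is not mentioned.

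**The concern.** The D28 scan is done for the trial: section 11.6 uses it to look for radiological changes in the lungs, and section 6.3 expects no direct benefit to volunteers. Section 6.3 also acknowledges that the scan carries a radiation risk to them. The protocol links vaccination and bronchoscopy to a same-visit pregnancy test and a stop rule, but not this scan, and gives no reason for the difference.

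Section 9.10 acts on a confirmed pregnancy, yet after D7 no scheduled test would confirm one. If a pregnancy did come to light, the section limits blood sampling but leaves open whether the CT goes ahead. A volunteer with an unrecognised pregnancy could therefore have a research scan without any departure from the protocol. What is at stake is participant safety at one procedure, not the validity of any result.

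**Working it through.** The plan states no figure for this interval, so there is none to reproduce. The check is date arithmetic on Table 1.

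**Inputs (Table 1, section 4.2)**
- Nominal days: pregnancy tests at screening, D0 and D7; next visits D14 and D28; CT at screening and D28.
- Windows: D14 ±4 days, D28 ±7 days.
- Anchor: each window runs from the actual date of the previous visit (table footnote).

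**Gap from the last scheduled test to the scan**
- Nominal: 28 − 7 = 21 days.
- D7 to D14: 7 ± 4 = 3 to 11 days.
- D14 to D28: 14 ± 7 = 7 to 21 days.
- Chained: 3 + 7 = 10 days to 11 + 21 = 32 days.

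If all windows ran from D0, the range would be (28 − 7) − (7 + 4) = 10 to (28 + 7) − (7 − 2) = 30 days. The footnote specifies chaining, so 10 to 32 applies.

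Two conditions attach. The D7 test must be done in its window; 9.9 allows bronchoscopy to be postponed by up to 3 weeks, and the documents do not say how the test and later visits would then move. The scan must also fall on the D28 visit date, which 9.5 makes usual but not certain.

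**What a test on the scan day would add**

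Let L be the time from conception to a positive urine test (not given in the documents).
- The D7 test can detect conceptions up to day 7 − L.
- A test on the day of a D28 scan can detect them up to day 28 − L.
- Gain = (28 − L) − (7 − L) = 21 days, whatever L is. Over the chained range the gain is 10 to 32 days.
- Conceptions in the last L days before the scan stay undetected either way.

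**Rough size of the yield**

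The number of women is not given. As an upper bound, take all 9 planned volunteers as women: 9 × 21 = 189 woman-days, and 189 / 365 = 0.52 woman-years. Assume 1% to 15% pregnancies per woman-year on the contraception accepted in section 8.3 (an assumption; the documents give no rate). The extra test would then be expected to find 0.52 × 0.01 = 0.005 to 0.52 × 0.15 = 0.08 pregnancies in the whole trial.

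**The case against.** The strongest reply is that the risk is already low and the protocol has several safeguards. Female volunteers must use effective contraception (8.2), and intended pregnancy is an exclusion (8.3). Adverse events are reviewed at D14 and D28, history can be taken at both, and a clinic assessment usually precedes the scan. Investigators may add tests (9.5). Section 9.10 allows withdrawal for confirmed pregnancy, and also for ineligibility arising during the trial, which pregnancy would be. Site-specific SOPs (14.1) may already require a check before imaging. On the rough figures above, the added test would most likely find nothing.

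Most of this stands, and it sets the weight of the point. But none of it puts a test before the scan: the history, withdrawal and extra tests are discretionary, and the SOPs are not in the documents. Contraception was not treated as enough at D0 and D7, where tests are scheduled.

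A fair challenge on scope is that the screening CT is also done at a re-attendance after the screening test (9.4), with no stated limit between the two. That is correct, although 9.4 books that scan only if no exclusion has been met, and pregnancy is one. The same sentence can cover both scans.

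A reader might infer more than the documents support:
- That no pregnancy test precedes the D28 scan. Three do; none is scheduled after D7.
- That a pregnant volunteer would be scanned. Section 9.10 continues follow-up under the protocol but does not say that this includes CT; it is silent.
- That sites make no check. The SOPs are unseen, so this cannot be said.
- That a fetal dose or harm can be quantified. The 2 mSv in section 6.3 describes exposure of the volunteer.

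**Conclusion.** The point holds as a small gap in participant safety that is cheap to close. The protocol schedules no pregnancy test after D7 and before a trial-mandated CT, and has no rule for a positive result at that scan. The interval is 21 days nominal, or 10 to 32 days with chained windows, given a D7 test in its window and a scan on the D28 visit date. A test on the scan day would extend detection by that same interval, whatever the detection lag, but would still miss very recent conceptions.

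The practical yield is very small: well under one pregnancy expected in a trial of 6 to 9 volunteers on contraception, under the assumed rates. No endpoint, analysis or conclusion of the trial is affected. This is something to consider at the next amendment.

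**What to change.** In Table 1, mark the urine pregnancy test at D28 for female volunteers, to be done on the day of the scan and before it, including when the clinic assessment is on another day. In section 9.5 (D28) or beside 9.9, add one sentence: a trial CT does not proceed after a positive pregnancy test, and section 9.10 then applies. Worded for any trial CT, with the test on the scan day, it also covers the screening scan.

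For the D28 scan the cost is one urine test per female volunteer: at most about 9 at the planned enrolment, plus any replacements, since "Volunteers withdrawn from the trial may be replaced on the decision of the Investigator". Covering the screening CT with a same-day test would add one test for each woman scanned at screening. No extra blood is needed, and no extra visit, because the volunteer already attends for the scan. The downside is that a positive result at D28 loses that volunteer's CT safety reading under 11.6.
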